### **13.5 Secondary Objectives, Endpoints, Analysis Plans**

The secondary objectives of the study include evaluation of the toxicity profile of nelipecimut-S vaccine and to compare the toxicity profile between the two groups. Additional secondary objectives include presence of DCIS at resection, difference in HER2 expression in the biopsy and the surgical specimen

excised post-vaccination and histologic responses (degree of lymphocyte infiltration determined on H&E stained slides as well as immune infiltration as determined by multiplex immunofluorescence staining for markers including but not limited to CD3, CD4 and CD8). Comparisons of intraperson changes in the vaccination versus GM-CSF alone arms will be made.

Adverse events by grade and relationship will be summarized by tabulation for each group. Correlation among the biomarkers described above at baseline in each specimen and between different specimens will be assessed. The association among various continuous and discrete biomarkers or treatment groups will be assessed by the exploratory data analysis using scatter plot matrix, box plots, BLiP plot [10] and trellis plot, etc., and may be tested by t-test/ANOVA/Wilcoxon rank sum test/Kruskal-Wallis test, when appropriate. Correlation between continuous biomarkers will be examined by Pearson or Spearman rank correlation coefficients. The association between discrete biomarkers will be tested by chi-square or Fisher's exact test. Paired t-test/Wilcoxon rank sum test and McNemar's test may be used to test the change of a single continuous biomarker and discrete biomarker, respectively, over time within each treatment group. Repeated measures analysis including mixed effects model will be performed to analyze the effect of treatment on biomarkers change over time [35].

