### 1.2 Secondary Objectives

- 1.2.1 Toxicity profile and frequency of adverse events in women with DCIS of the breast receiving nelipecimut-S vaccine as compared to women receiving GM-CSF alone;
- 1.2.2 Presence of DCIS at resection;
- 1.2.3 Difference in HER2 expression in the biopsy and the surgical specimen excised post-vaccination;
- 1.2.4 Histologic responses:
- 1.2.4.1 Degree of lymphocyte infiltration determined on H&E stained slides and immune infiltration as determined by multiplex immunofluorescence staining for markers including but not limited to CD3, CD4 and CD8;
- 1.2.4.2 Immune infiltrates in normal tissue maximally distant from the tumor (in mastectomy samples).

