Dose Reductions of Vaccine. Toxicities observed with the vaccine are attributable to the GM-CSF. Although the toxicity profile of GM-CSF is the same for a 250 µg dose as for a 125 µg dose, the extent of the toxicity will vary between participants. Therefore, the provision for dose reductions of the GM-CSF component of the vaccine is a safety issue for an individual participant. For participants experiencing robust local reactions (>100mm x 100mm); grade 3 local reactions; or greater than or equal to grade 2 hypersensitivity reactions the dose of GM-CSF will be reduced for the subsequent inoculation as outlined in Table 1 below. This dose reduction will be done to decrease the likelihood that the participant will experience the same degree of reaction. Management of hypersensitivity reactions will be at the discretion of the Investigator or an appropriately qualified member of the study team designated by the Investigator.

Dose Reduction of GM-CSF.

*Table 1. Dose Reduction Using Reconstituted Lyophilized Leukine*

	Amount of reconstituted Leukine® solution removed prior to addition of E75 acetate solution	Amount of WFI diluent added back to E75 acetate solution	Dose of rhGM-CSF
No dose reduction	0 mL	0 mL	250 µg
1 st dose reduction	0.5 mL	0.5 mL	125 µg

In our prior trial, approximately 5% of patients developed delayed urticarial reactions (generalized urticaria 10-14 days after booster inoculation). This was not seen during the primary vaccination series.

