### **13.7 Evaluation of Toxicity**

All participants will be evaluable for toxicity from the time of their first vaccination. The toxicity profile in terms of type, attribute, and grade of toxicities will be described in each of the treatment arms.

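### Toxicity is to be compared between vaccine and GM-CSF alone, but the plan specifies only per-arm tables, with no between-arm difference, no interval and no counting unit

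*Combined protocol and SAP*

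**What the plan says.** The objective is comparative wherever it appears. Section 1.2.1 asks for the toxicity profile and the "frequency of adverse events in women with DCIS of the breast receiving nelipecimut-S vaccine as compared to women receiving GM-CSF alone". Section 8.2.1 and the schema say the same, and Section 13.5 restates the aim as "to compare the toxicity profile between the two groups".

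Two sentences give the analysis of adverse events (AEs). Section 13.5: "Adverse events by grade and relationship will be summarized by tabulation for each group". Section 13.7: "The toxicity profile in terms of type, attribute, and grade of toxicities will be described in each of the treatment arms".

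The tests listed in Section 13.5 are for other variables, for example "The association between discrete biomarkers will be tested by chi-square or Fisher's exact test". The comparison of within-person changes between arms follows the tissue endpoints. One exploratory sentence mentions treatment groups, but it concerns biomarkers, is permissive and does not name AEs.

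Sections 5.7 and 13.8 define the safety set as women who received at least one vaccination. The decision rule in Section 13.1 has a 10% ceiling on grade III AEs attributed to the active drug and grade IV AEs of any attribution, with no reference to the control arm.

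**The concern.** The control arm receives the adjuvant, so the randomised difference between arms measures directly what the peptide adds. Section 2.3 gives this as a reason for the control, including for the secondary endpoints. The plan nevertheless stops at one table per arm.

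This matters because the protocol already leans towards an answer. Section 5.6 says "Toxicities observed with the vaccine are attributable to the GM-CSF", while Section 2.3 reports two hypersensitivity reactions in the phase III trial that were judged definitely related to study drug. Section 2.3 also says that completing the trial will establish safety and support a larger DCIS study and a prevention trial. A table split by relationship depends on a causality judgement, and Section 6.9.2 leaves investigators unblinded. An all-cause difference between arms does not need the attribution to study agent, although unblinded ascertainment can still affect it.

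At stake is the weight that a safety statement from 48 women can bear.

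**Working it through.** **1. The plan's own figure.** The only power or precision stated is 82% for the CTL endpoint (Section 13.1: 27 v 13, effect size 1, two-sided 0.05). Noncentrality is 1/√(1/27 + 1/13) = 2.96 with 38 degrees of freedom and critical value 2.02. Power is 82.3%, so the figure reproduces. It says nothing about toxicity, for which the documents give no power, precision or margin.

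**2. Size of the safety set.** Section 13.2 randomises 48 women 2:1, so 48 × 2/3 = 32 vaccine and 48 × 1/3 = 16 control. These are maxima. Fewer treated women would widen the intervals.

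**3. What equal-looking tables allow.** I used the Newcombe interval for a difference in proportions. For each arm the Wilson limits (l, u) are

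[p + z²/2n ± z√(p(1−p)/n + z²/4n²)] / (1 + z²/n), with z = 1.96.

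With d = p₁ − p₂ (vaccine minus control):

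- lower limit = d − √[(p₁ − l₁)² + (u₂ − p₂)²]
- upper limit = d + √[(u₁ − p₁)² + (p₂ − l₂)²]

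Worked case, 8/32 v 4/16. Wilson limits are 0.133 to 0.421 (vaccine) and 0.102 to 0.495 (control), and d = 0.

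- Lower: −√[(0.250 − 0.133)² + (0.495 − 0.250)²] = −0.272
- Upper: +√[(0.421 − 0.250)² + (0.250 − 0.102)²] = +0.226

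| Vaccine | Control | Difference | 95% CI (percentage points) |
|---|---|---|---|
| 0/32 | 0/16 | 0 | −19 to +11 |
| 2/32 | 1/16 | 0 | −23 to +15 |
| 4/32 | 2/16 | 0 | −25 to +18 |
| 8/32 | 4/16 | 0 | −27 to +23 |
| 16/32 | 8/16 | 0 | −27 to +27 |

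In these cases identical observed rates are compatible with about 11 to 27 points of added toxicity.

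**4. How often a real excess would not show.** The documents give no rates for GM-CSF alone, so control rates here are assumptions. With a true excess of 10 points, the observed vaccine rate would be equal to or below the control rate in about 10% of trials (2% v 12%), 20% (10% v 20%) or 25% (19% v 29%).

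**5. Would a test help?** Exact power of the two-sided Fisher test at 32 v 16, for assumed control rates of 2% to 50%, is 2% to 8% for a 10-point excess, 21% to 31% for 20 points and 44% to 73% for 30 points. A test would add little; an estimate with its interval is the useful summary.

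**The case against.** Descriptive safety reporting is a defensible choice in a 48-woman phase II trial powered only on CTL change. Both arms are tabulated, so a reader could take a crude difference from the tables. All-cause totals can be recovered by adding the relationship categories, since Section 11.1.1 records AEs whether or not related to study agent. The go rule does not depend on similarity between arms. The intervals above also show that the contrast would be imprecise.

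Much of this stands, and it rules out three stronger readings that a reader might infer:

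- *That the peptide's added toxicity could not be obtained.* The documents do not support this, because data from both arms will be shown. What is missing is a pre-specified contrast with its uncertainty.
- *That the tables count events, so the larger arm would look more toxic.* Neither Section 13.5 nor Section 13.7 states a unit, and earlier toxicity in Section 2.3 is given as percentages of participants. The fair criticism is that the unit is unspecified.
- *That the plan will treat similar tables as no added toxicity.* No section says so. The Section 5.6 sentence about GM-CSF explains dose reductions and is not an analysis assumption; Section 6.2 says only that effects are likely attributable to GM-CSF.

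The objection does not close the gap between an objective that compares and an analysis that describes. Section 8.2.2 labels its DCIS data descriptive only and explains why; nothing similar is said for toxicity. Imprecision is a reason to show the interval.

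**Conclusion.** The point holds in limited form. The plan sets a between-arm toxicity objective and pre-specifies no contrast, no uncertainty and no counting unit to answer it. At 32 v 16, the equal observed rates examined leave upper limits of +11 to +27 points, so tables alone cannot establish that the peptide adds little.

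This rests on the maximum safety set, on counting women rather than events, and on the Newcombe method. The interval widths need no assumed event rates; the figures in steps 4 and 5 of the working do. The risk that similar tables are misread is a judgement about readers. The primary analysis, the sample size and the go rule are unaffected, so this is a change that should be made but not one that threatens the trial.

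**What to change.** In Sections 13.5 and 13.7:

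1. Count each woman once at her worst grade, with women who received at least one vaccination as the denominator in each arm.
2. Add the vaccine-minus-control difference in proportions with a 95% CI (for example Newcombe), descriptive and without a test, for a short pre-specified list regardless of attribution to study agent. One possible list is any grade ≥2 AE, any grade ≥3 AE and any grade ≥2 injection-site reaction. The study team should settle the list before looking at data by arm.
3. State that any conclusion on similarity of toxicity rests on the interval and not on the tables alone.
4. Note that under Section 11.1.1.2, from the day of surgery to the post-vaccination visit, only AEs judged not related to surgery are recorded. The all-cause rows therefore still carry that judgement.

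The cost is a few lines of text and a few table rows, with no new data. The downside is that wide intervals will openly limit the safety claim.

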### 8.2 Secondary Endpoints

Secondary endpoints include:

8.2.1 Toxicity profile and frequency of adverse events in women with DCIS of the breast receiving nelipepimut-S vaccine as compared to women receiving GM-CSF alone.

- 8.2.2 Presence of DCIS at resection. The histologic data will be presented in tabular form to examine whether the vaccine treatment is associated with the absence of DCIS, induction of necrosis, reduction in histologic grade, or a reduction in the size of DCIS. These data will be descriptive only. The data will be obtained from the standard surgical pathology report generated as part of the patient’s clinical care. Formal comparisons of these parameters would likely require a larger sample size to see a statistically significant difference in presence of DCIS, induction of necrosis, or reduction in size of DCIS.
- 8.2.3 Difference in HER2 expression in the biopsy and the surgical specimen excised post-vaccination. HER2 scoring will be determined according to the American Society of Clinical Oncology/College of American Pathologists clinical guidelines [7]. Positive cases are those with circumferential membrane staining that is complete, intense, and within >10% of tumor cells (Score 3+). Negative cases are defined as those with no observable staining, or membrane staining that is incomplete and is faint/barely perceptible and within less than or equal to 10% of tumor cells (Score 0) or incomplete membrane staining that is faint/barely perceptible and within >10% of tumor cells (Score 1+). Equivocal or indeterminate cases are those with circumferential membrane staining that is incomplete and or weak/moderate and within >10% of tumor cells or complete and circumferential membrane staining that is intense and within less than or equal to 10% of tumor cells (Score 2+). Pre-vaccination and post-vaccination specimens will be compared.
- 8.2.4 Degree of lymphocyte infiltration. We will define intra-tumoral TIL as those within the basement membrane. Stromal TIL will be defined as those in the periductal/lobular stroma including the intralobular stromal infiltrate. Cells in the interlobular stromal inflammatory infiltrate will be excluded. All mononuclear cells will be scored but polymorphonuclear leukocytes will be excluded. Intra-tumoral and stromal TILs will be scored as a continuous variable and the percentage of in the surgical specimen will be compared to that in the pre-vaccination diagnostic biopsy.

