### **13.4 Primary Objective, Endpoint, Analysis Plan**

The primary objective of this study is to evaluate the effect of the nelipecimut-S vaccine on nelipecimut-S-specific CTL measured in blood in DCIS participants that are HLA-A2 positive. We will use a dextramer assay, which is a flow cytometry based assay, to enumerate the number of nelipecimut-S-specific CTL generated in response to vaccination with the nelipecimut-S peptide. The number of nelipecimut-S-CTL will be determined in participants at the following time points: pre-vaccination, at the time of surgery (after two preoperative vaccinations), 1 month (+/- 7 days) after surgery, and 3-6 months after surgery at the time of the final study visit. The change in the number of nelipecimut-S-CTL for an individual participant between the pre-vaccination timepoint and the 1 month (+/- 7 days) after surgery timepoint will be used as the primary endpoint measure for this study.

At the end of the study, the change of nelipecimut-S-specific CTL at the 1 month (+/- 7 days) after completion of the vaccination series timepoint from baseline will be estimated for each group using mean, standard deviation, median, minimum and maximum. Two-sample t-test or Wilcoxon rank sum test, whichever appropriate, will be used to compare the change between the two groups. Nelipecimut-S-specific CTL will also be measured repeatedly through 3 months after surgery. Repeated measures analysis including mixed effects model will be performed to analyze the effect of treatment on nelipecimut-S-specific CTL change over time [35]. We will evaluate the results in the whole participant population as well as the participants with or without radiation treatment separately, when appropriate

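### Section 13.5 names the Wilcoxon rank sum test for paired within-arm change; the signed-rank test is the paired counterpart (minor wording correction)

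*Combined protocol and SAP*

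**What the plan says.** Section 13.5 deals with change within an arm in one sentence. Its list of tests begins "Paired t-test/Wilcoxon rank sum test and", where the first two are meant for a continuous biomarker and McNemar's test, named next, for a discrete one. The sentence makes these tests optional and gives their setting as change "over time within each treatment group".

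The same test name appears in two other places, both times for independent groups:

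- Section 13.4, primary endpoint: "Two-sample t-test or Wilcoxon rank sum test, whichever appropriate, will be used to compare the change between the two groups".
- Section 13.5, earlier in the same paragraph, on association among biomarkers or treatment groups: "may be tested by t-test/ANOVA/Wilcoxon rank sum test/Kruskal-Wallis test, when appropriate".

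The signed-rank test is not named anywhere in the supplied text. The tissue data to which the within-arm sentence would naturally apply are paired. Section 8.2.4 scores tumour-infiltrating lymphocytes (TILs) as a continuous variable, and the percentage "in the surgical specimen will be compared to that in the pre-vaccination diagnostic biopsy". Sections 5.7 and 13.8 make the full endpoint evaluation depend on paired biopsies being available.

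**The concern.** Change over time within one arm is a paired comparison: each woman supplies a before value and an after value. The paired t-test and McNemar's test in the sentence are both paired methods. The rank sum test is not. It treats the before values and the after values as two unrelated samples and takes its null variance from that assumption.

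The variance is wrong whenever a woman's two values are correlated. With positive correlation it is too large, so the test is conservative and misses real change. With negative correlation it is too small, so the test rejects too often. A nonparametric fallback could well be needed here, because a TIL score is a percentage and the control arm is small. An analyst who follows the sentence as written would lose information in a small trial. An analyst who runs the correct test would depart from the plan.

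**Working it through.** **1. The plan's own figure.** Section 13.1 gives 82% power for the primary between-arm comparison, with 27 and 13 women, effect size 1 and two-sided 5%. For the two-sample t-test, df = 27 + 13 - 2 = 38 and the noncentrality is 1/sqrt(1/27 + 1/13) = 2.96. The noncentral t distribution gives 82.3%, so the stated figure reproduces. It rests on a between-arm test and does not depend on the sentence at issue. Section 13.5 states no figure for the within-arm tests.

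**2. Inputs for the illustration.** All of these are assumptions, because the documents give no correlation, effect size or number of pairs for the tissue data.

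- Number of pairs: 27 and 13. These are the expected evaluable counts for the blood CTL endpoint in Section 13.1, used as stand-ins.
- Distribution: bivariate normal, with equal SD before and after.
- Shift: 0 (null) or 0.5 SD of a single measurement.
- Within-woman correlation r: -0.3, 0, 0.3, 0.5 and 0.7.

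**3. Simulation.** There were 20,000 data sets per setting, tested at two-sided 5%. The rank sum test used the normal approximation with continuity correction, and the signed-rank test used its exact null distribution. Each cell shows rank sum / signed-rank.

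| r | Type I error, n = 27 | Power, n = 27 | Type I error, n = 13 | Power, n = 13 |
|---|---|---|---|---|
| -0.3 | 8.2% / 5.1% | 41.8% / 32.2% | 7.3% / 4.9% | 24.0% / 17.0% |
| 0 | 4.8% / 5.0% | 41.2% / 40.8% | 4.5% / 4.8% | 20.6% / 20.7% |
| 0.3 | 2.0% / 4.7% | 39.9% / 53.7% | 1.9% / 4.7% | 16.9% / 27.1% |
| 0.5 | 0.7% / 4.9% | 39.1% / 68.1% | 0.8% / 4.8% | 14.4% / 36.1% |
| 0.7 | 0.1% / 5.1% | 37.4% / 88.5% | 0.2% / 4.8% | 11.0% / 54.6% |

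The higher rank sum rejection rate under the shift at r = -0.3 comes from its inflated type I error and is not a real gain in power.

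**4. Analytic check.** Pairing multiplies the null variance of the rank sum statistic by about 1 - rho_S, where rho_S is the Spearman correlation. For normal data, rho_S = (6/pi) arcsin(r/2). The actual type I error is then about 2 P(Z > 1.96 / sqrt(1 - rho_S)).

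- At r = 0.5: rho_S = 0.483, 1.96/sqrt(0.517) = 2.72, type I error 0.6%.
- At r = -0.3: rho_S = -0.288, 1.96/sqrt(1.288) = 1.73, type I error 8.4%.
- At r = 0, 0.3 and 0.7: 5.0%, 2.0% and 0.05%.

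These agree with the simulated values for n = 27.

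**5. Second simulation.** A separate run of 10,000 data sets at non-negative correlations gave, for n = 27 and r = 0.5, type I error of 0.8% (rank sum) and 5.1% (signed-rank), and power of 39% and 69%. The paired t-test had 70% power in the same setting. At r = 0 the type I errors were 4.7% and 5.1%.

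**The case against.** The strongest reply is that this is a slip of the pen and not a choice of method. The sentence opens with a paired test and closes with another, and its stated purpose is change within an arm. If the variable analysed is each woman's change, one arm gives a single sample and a rank sum test has nothing to compare it with. A competent analyst would read it as signed-rank. The sentence is also permissive, and a valid paired test is already named first. Section 13.5 commits separately to between-arm comparison of within-person changes and to mixed models, and both respect the pairing. HER2 score and presence of DCIS are not continuous, so the slip does not govern them. Section 8.2.4 itself names no test. The numbers above rest on assumed correlations, an assumed shift and stand-in counts, and nothing in the documents points to a negative correlation.

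Most of this stands, and it is why the point is minor. It does not remove the error. The plan gives the term its independent-samples meaning twice elsewhere, so a reader cannot take it to mean signed-rank by local convention, and no other section corrects it. The negative-correlation case shows the direction of the error and is not a forecast for this trial.

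**Conclusion.** The concern holds, as a minor wording error in an operative analysis rule. The rank sum test is the wrong named counterpart to the paired t-test for within-arm change.

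The effect, if the sentence is followed literally, depends on the within-woman correlation, which the documents do not give. For positive correlations of 0.3 to 0.7 with 27 pairs, type I error falls to between 2.0% and 0.1%, and power for a 0.5 SD shift stays at about 37% to 40%, where the signed-rank test has 54% to 89%. At zero correlation nothing is lost. At a negative correlation the test would be too liberal. These figures assume normal data and use blood-endpoint counts in place of tissue pairs. Confidence in the wording point is high. Whether it would change any reported result cannot be known from the documents.

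The primary test, the 82% power, the decision rule in Section 13.1, the between-arm comparisons and the mixed models are untouched.

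**What to change.** In the within-arm sentence of Section 13.5, replace Wilcoxon rank sum test with Wilcoxon signed-rank test. Keep the rank sum test in Section 13.4 and in the earlier sentence of Section 13.5. It is valid there for comparing independent groups, including a comparison of each woman's change between arms.

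The cost is one term in one sentence. Data collection, sample size and procedures do not change.
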